## 5. BASELINE CHARACTERISTICS

### 5.1. Demographics and Baseline Characteristics

Subject demographic variables (ie, age, age group [ $<40/\geq 40$  years], sex, race, and ethnicity), baseline characteristics (body weight [in kg], height [in m], body mass index [BMI; in  $\text{kg}/\text{m}^2$ ]) will be summarized by treatment group and overall using descriptive statistics for continuous variables and using number and percentage of subjects for categorical variables. The summary of demographic data will be provided for the Safety Analysis Set.

A by-subject demographic listing, including the informed consent date, will be provided by subject ID number in ascending order.

### 5.2. Baseline Disease Characteristics

Baseline disease characteristics will be summarized by treatment group and overall. Summary descriptive statistics will be used for continuous variables and the number and percentage of subjects will be used for categorical variables. The following factors will be included, but not limited to:

- Years positive for HBV
- HBV Genotype
- Baseline NrtI type
- Years on current HBV treatment
- Baseline HBV DNA ( $\log_{10}$  IU/mL)
- Baseline HBV RNA ( $\log_{10}$  U/mL)
- Baseline HBV total nucleic acid (TNA) ( $\log_{10}$  IU/mL)
- Baseline HBeAg ( $\log_{10}$  IU/mL)
- Baseline HBcrAg ( $\log_{10}$  kU/mL)
- HBcrAg groups ( $< \text{LLOQ}$ ,  $< 500$ ,  $< 100$ ,  $< 10$ )
- Baseline HBsAg ( $\log_{10}$  IU/mL)
- HBsAg groups ( $< \text{LLOQ}$ ,  $\leq 1000$ ,  $> 1000$  IU/mL)
- Baseline HBeAg antibody (HBeAb)

- Baseline HBsAg antibody (HBsAb)
- Baseline ALT (U/L)
- Baseline ALT groups (>ULN [Covance], >ULN [American Association for the Study of Liver Diseases (AASLD)])
- Liver biopsy staging
- Fibroscan result
- Metavir Fibrosis Stage

A by-subject listing of baseline disease characteristics will be provided by subject ID number in ascending order.

### **5.3. Medical History**

Medical history collected at Screening will be coded using the Medical Dictionary for Regulatory Activities (MedDRA) Version (v) 23.1.

Medical history will be summarized by preferred term (PT), treatment group and overall. Subjects who report 2 or more medical history items that are coded to the same PT will be counted only once by the unique coded term in the summary. The summary will be provided for the Safety Analysis Set.

HBV specific medical history will be summarized by mode of HBV infection, treatment group and overall. The summary will be provided for the Safety Analysis Set.

A by-subject listing of medical history will be provided by subject ID number in ascending order.

## **6. EFFICACY ANALYSES**

The primary analysis set for efficacy analyses will be the FAS, defined in Section 3.1.2. All the efficacy analyses will be performed for each cohort separately. The following sections describe the primary and secondary analyses for the efficacy endpoints.

### **6.1. Efficacy Endpoints**

#### **6.1.1. Definition of Efficacy Endpoints**

The efficacy endpoints of Cohort 1 are:

- Mean change in  $\log_{10}$  HBsAg from Baseline at each timepoint
- Mean change in  $\log_{10}$  HBV RNA from Baseline at each timepoint
- Mean change in  $\log_{10}$  HBcrAg from Baseline at each timepoint
- Mean change in TNA quantitative from Baseline at each timepoint
- ALT results and change from Baseline

#### **6.1.2. Analysis Methods for Efficacy Endpoints**

The observed and mean change in  $\log_{10}$  HBV RNA, HBV TNA, HBsAg, HBcrAg, and ALT from Baseline will be summarized using descriptive statistics (sample size, mean, SD, median, Q1, Q3, minimum, and maximum) by phase, treatment group, and treatment action at each visit.

For the On-Treatment Phase, analysis will be performed to compare the mean changes of  $\log_{10}$  HBV RNA,  $\log_{10}$  HBV TNA,  $\log_{10}$  HBsAg,  $\log_{10}$  HBcrAg, and ALT from Baseline to each timepoint between VBR+AB-729+NrtI and VBR+NrtI, and between VBR+AB-729+NrtI and AB-729+NrtI. The primary comparison for mean change endpoints will be made using an analysis of covariance (ANCOVA) model, including baseline value, the stratification factors, and treatment group as covariates. The estimated least square means of treatment effects and estimated difference in treatment effects between treatment groups at Week 48 will be presented along with the 95% CIs and p-values. The analysis will be based on observed data.

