### 7.2 Criteria for Discontinuation of Study Treatment

With the exception of treatment cessation based on Treatment Stopping Criteria (see [Section 4.1.1](#)), study drug treatment may be discontinued in the following instances:

- Intercurrent illness that would, in the judgement of the Investigator, affect assessments of clinical status to a significant degree
- Unacceptable toxicity as defined in [Section 9.10](#) (Toxicity Management), or toxicity that, in the judgment of the Investigator, compromises the ability to continue study-specific procedures or is considered to not be in the subject's best interest
- Lack of efficacy (virologic failure)
- Subject noncompliance
- Pregnancy during the study
- Discontinuation of the study at the request of the Sponsor, a regulatory agency or an Institutional Review Board or Independent Ethics Committee (IRB/IEC)

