    - If ALT is rising at the confirmatory visit, subjects should return for an Unscheduled Visit every 2 to 5 days until the ALT elevation has stabilized. At these visits, the following laboratory tests will be performed: ALT, AST, total bilirubin (if total bilirubin is elevated, reflex to direct bilirubin), serum albumin, INR, creatine kinase, HBV DNA, quantitative HBV serologies (HBeAg [reflex qualitative HBeAg if quantitative HBeAg is negative] and HBsAg [reflex qualitative HBsAg if quantitative HBsAg is negative]). The Investigator will determine if other assessments specified in [Section 8.4](#) should be performed. Subjects whose ALT has stabilized should continue to be monitored weekly (or more frequently, as deemed necessary by the Investigator) until ALT values return to normal or Baseline levels.
    - Subjects with an ALT elevation without declining hepatic function and without contraindications should discontinue study drug if the ALT remains persistently elevated for  $>4$  weeks
- ALT Elevation With Declining Hepatic Function

[figure not shown]
- Subjects with confirmed ALT elevation with biochemical evidence of declining hepatic function should be discontinued from study treatment. This is defined as:
  - ALT elevation  $\geq 2 \times$  Baseline or nadir and  $> 2 \times$  ULN AND
    - Direct bilirubin increase to  $\geq 2 \times$  Baseline and  $\geq 2 \times$  ULN OR
    - Albumin decline  $\geq 0.5$  g/dL OR INR  $> 1.5 \times$  Baseline OR
    - Symptoms of liver inflammation (eg, fatigue, weakness, lack of appetite, nausea, vomiting, jaundice, or discolored feces)
- Subjects with evidence of declining hepatic function should return for an Unscheduled Visit every 2 to 5 days until the relevant laboratory values stabilize. Subjects whose hepatic function has stabilized should continue to be monitored weekly (or more frequently as deemed necessary by the Investigator) until the relevant laboratory values return to normal or Baseline.

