##### **3.1.2. Full Analysis Set**

The Full Analysis Set (FAS) includes all randomized subjects, classified according to the treatment group into which they were randomized regardless of the actual treatment received who took at least 1 dose of a study drug. This is the primary analysis set for efficacy analyses.

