### **3.5. Missing Data and Outliers**

#### **3.5.1. Missing Data**

In general, missing data will not be imputed unless methods for handling missing data are specified. Exceptions are presented in this document.

For missing last dose date of study drug, imputation rules are described in [Section 4.2.1](#). The handling of missing or incomplete dates for adverse event (AE) onset is described in [Section 7.1.5.2](#), and for prior and concomitant medications in [Section 7.3.2](#).

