#### **3.6.3. Definition of Study Phase and End of Study**

The analyses will include all the data collected in this study based on three phases defined as follows.

- **On-Treatment Phase:** when a subject is undergoing treatment with AB-729, VBR, or both per treatment group (ie, from first dose of either study drug through the last dose of VBR +1 day or last dose of AB-729 +56 days, whichever is later)
- **Off-Treatment Phase:** after a subject has discontinued AB-729, VBR, or both per treatment group, and prior to NrtI restart if applicable (ie, after the last dose of VBR +1 day or last dose of AB-729 +56 days, whichever is later, until the end of study or before the first dose of NrtI if it was restarted)
- **NrtI-Restart Phase:** after a subject has restarted NrtI, following the Off-Treatment Phase (ie, from the first dose of restarted NrtI through the end of study)

End of study is defined as when the last subject completes the last follow-up or is considered “lost to follow-up”, whichever is later.

Subjects may prematurely discontinue study drug earlier prior to the Week 48 visit. The end dates of the On-Treatment Phase may vary for individual subjects based on their last dose dates as defined in [Section 3.6.3](#).

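### The Week 48 ANCOVA uses observed on-treatment values only, so subjects who stop all study drug early, including for ALT, usually drop out of the contrasts, and by a rule that differs between arms

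*Combined protocol and SAP*

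**What the plan says.** SAP 6.1.2 sets the comparison: "For the On-Treatment Phase, analysis will be performed to compare the mean changes of" log10 HBV RNA, TNA, HBsAg, HBcrAg and ALT, for the triple arm against each dual arm. "The primary comparison for mean change endpoints will be made using an analysis of covariance (ANCOVA) model" with baseline, stratum and treatment; Week 48 differences are reported with 95% CIs and p-values. The section ends: "The analysis will be based on observed data".

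The efficacy population is the Full Analysis Set (SAP 3.1.2), that is, subjects randomized and dosed, grouped as randomized: "This is the primary analysis set for efficacy analyses". On missing values, SAP 3.5.1 says: "In general, missing data will not be imputed unless methods for handling missing data are specified". The exceptions it lists concern dates. Protocol 10.6 leaves missing-data methods to the SAP.

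SAP 3.6.3 defines the On-Treatment Phase as the time "when a subject is undergoing treatment with AB-729, VBR, or both per treatment group", closing 1 day after the last VBR dose or 56 days after the last AB-729 dose, whichever is later. SAP 3.6.5 instead describes on-treatment data as running to the Week 48 or premature termination visit.

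Under protocol 9.10.4, a subject with an ALT elevation but no decline in hepatic function "should discontinue study drug if the ALT remains persistently elevated for" more than 4 weeks; one with declining function should also be discontinued. Table 9, footnote a, sends early stoppers to a Premature Termination visit and then to the Weeks 52 to 96 schedule.

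**The concern.** Put together, these rules make presence in the Week 48 contrast depend on still being on study drug, and one reason for leaving study drug is itself an endpoint of the contrast. The ANCOVA then estimates mean change among subjects still on treatment at Week 48. The stated objective is the effect of adding VBR and AB-729 to NrtI, and the result would carry the Full Analysis Set label. Removing subjects with high ALT flatters the arm they came from. With dual arms of 15, one or two subjects matter. Because the phase closes at different times in different arms, the same early stop can be excluded in one arm and kept in another.

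**Working it through.** **No planned figure to reproduce.** The sample size has no effect size, SD, power or dropout rate behind it. Only the split can be checked: 60 × (2, 1, 1)/4 = 30, 15, 15, as in protocol Table 7.

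**Step 1: who has a Week 48 value.** For ALT, HBsAg, RNA and TNA the Week 48 window is Days 323 to 350 (SAP Table 3-1). Phase end = max(last VBR day + 1, last AB-729 day + 56). Counting 8-week steps from Day 1, injections fall on Days 1, 57, 113, 169, 225 and 281. The SAP's nominal day for Week 40 is 280, which moves the last phase end by one day and changes nothing below.

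| All study drug stopped | Last AB-729 | Phase end, Group 2 | Phase end, Group 1 |
|---|---|---|---|
| Day 150 | Day 113 | Day 151 | Day 169 |
| Day 280 | Day 225 | Day 281 | Day 281 |
| Day 300 | Day 281 | Day 301 | Day 337 |
| Day 322 | Day 281 | Day 323 | Day 337 |

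In Group 2, any stop before Day 322 closes the phase before the window opens. In Groups 1 and 3 the same holds for a stop before the Week 40 injection. After that injection the phase stays open to 281 + 56 = Day 337 in both groups (in Group 3 the AB-729 course is then complete), so a sample on Days 323 to 337 would count. The follow-up schedule for early stoppers lists no Week 48 visit, so such a sample would come from, for example, an unscheduled ALT visit. A Group 1 subject who stops only VBR and continues AB-729 stays on-treatment.

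**Step 2: the Premature Termination sample.** In Group 2, a sample taken more than 1 day after the last VBR dose is off-treatment under SAP 3.6.3 but appears to be on-treatment under SAP 3.6.5. Either way, a sample before Day 323 goes to the window of its own study day, so the Week 48 ANCOVA does not use it.

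**Step 3: leverage of one subject.** Protocol Table 4, Week 48, n = 12: mean ALT 29.6 (maximum 168), mean change -40.8 (maximum +148). The two maxima belong to one subject: the lowest baseline is 17, so a change of +148 means at least 165 U/L, and only one subject was above ULN.
- Mean ALT without that subject: (12 × 29.6 - 168)/11 = 17.0 U/L.
- Mean change without that subject: (12 × (-40.8) - 148)/11 = -58.0 U/L, a shift of 17.2.

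For this trial the inputs must be assumed. If one lost subject's ALT change lies 50 to 400 U/L above the rest, the arm mean shifts by excess/n: 50/15 to 400/15 = 3.3 to 26.7 U/L at n = 15, and 1.7 to 13.3 U/L at n = 30.

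**Step 4: precision.** With 27 and 13 instead of 30 and 15, the SE rises by sqrt(1/27 + 1/13)/sqrt(1/30 + 1/15) = 1.068, or 6.8%. The issue is bias, not power.

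**Step 5: how much a mixed model recovers.** Illustrative simulation of a log10 marker, 30 vs 15 subjects, 13 post-baseline visits, between-subject SD and error SD both 0.15. One of the 15 comparator subjects rises by 1 log10 over 12 weeks (random onset, Weeks 8 to 36) and is lost after two consecutive values above 0.5. The average Week 48 difference was -0.065 with all values, -0.005 on observed data and -0.023 from a mixed model. The model recovers (0.023 - 0.005)/(0.065 - 0.005) = 30% of the loss. The stopping rule and the rise are assumptions found in neither document; the run compares methods and does not forecast this trial.

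**The case against.** The strongest reply is that little is at stake. Efficacy is secondary, the sample size has no statistical basis, and SAP section 3 plans no formal testing. ALT elevations are tabulated in the safety analyses (SAP 7.2.1.2 and 7.2.3.2), SAP 6.1.2 shows n by visit, and SAP 4.1 gives discontinuation reasons by group. The precursor studies suggest few relevant stops: in Study 211, 90 of 92 subjects remained on treatment through 24 weeks and none stopped for ALT, and AB-729-001 reported no discontinuations for AEs. The termination in February 2023 is not itself a source of missing Week 48 data, because the SAP says every active subject had completed 48 weeks.

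This limits the severity. It does not repair the contrast: SAP 6.1.2 still reports a difference, CI and p-value, and the safety tables do not correct them.

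Three stronger readings are tempting, and the documents do not support them:
- A reader might infer that stops for virologic failure strip the worst values from the HBV RNA and TNA contrasts. Protocol 7.2 only permits such stops, and the one working definition (protocol 8.7) uses HBV DNA, which is not an ANCOVA endpoint. TNA may follow DNA, but the link is indirect. In Table 6 the largest RNA increase in HBeAg-negative subjects is 0.3 log10 at any visit and 0.1 at Week 48.
- A reader might take the Table 4 shift as a forecast. That subject was observed at Week 48. At 168 U/L, or 168/43 = 3.9 to 168/34 = 4.9 times ULN, the value is below the 10 × ULN that defines the elevation without declining function. The population was treatment-naïve and HBeAg positive.
- A reader might conclude that every early stopper is lost. Step 1 shows the exceptions, and all subjects stay in the windows they reached.

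**Conclusion.** The concern holds as a defect of method whose size is unknown. The rules remove most subjects who stop all study drug early from the Week 48 contrasts. For ALT that removal can depend on the outcome, and the cut-off of 1 day against 56 days treats the arms unequally. HBsAg, RNA and TNA lose the same subjects, without a direct link between those outcomes and the stop. The documents give no count of early stoppers; if none stopped for ALT or declining function, the bias from this source is zero. The shifts of 3.3 to 26.7 U/L per lost subject in an arm of 15 rest on an assumed excess at Week 48 and would be smaller if ALT fell after the stop. The documents do not support a claim that a treatment difference has been hidden or reversed.

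**What to change.** 1. In SAP 6.1.2, for HBsAg, HBV RNA, HBV TNA and ALT, estimate the Week 48 contrasts on the Full Analysis Set from a repeated-measures mixed model. Use all on-treatment visits plus the Premature Termination visit, with baseline, stratum and treatment-by-visit terms and a structured covariance fixed in advance. Keep the observed-data ANCOVA beside it. HBcrAg is outside this change: on treatment it is scheduled only at Day 1 and Week 48, apart from Premature Termination.
2. Reconcile SAP 3.6.3 with SAP 3.6.5 so that the Premature Termination sample counts as on-treatment under one rule in every arm.
3. Because the mixed model recovers only part of an outcome-related loss, add a labelled sensitivity analysis for the ALT contrast. For subjects stopped for ALT elevation or declining hepatic function, carry the last on-treatment or Premature Termination value to Week 48. State that this may overstate Week 48 ALT, since ALT can fall after the stop. Do not apply it to HBsAg, where a stop for ALT has no stated unfavourable meaning and the carried value could preserve an on-drug decline.
4. Print, by arm, the number of Full Analysis Set subjects without a Week 48 value and the reasons.

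No new data are needed. The cost is modest programming and a covariance structure chosen in advance. The SAP already provides for changes after finalization to be documented in the Synoptic CSR.

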## **7. SAFETY ANALYSES**

### **7.1. Adverse Events and Deaths**

#### **7.1.1. Adverse Event Dictionary**

Clinical and laboratory adverse events (AEs) will be coded using the Medical Dictionary for Regulatory Activities (MedDRA) Version (v) 23.1. System organ class (SOC), high-level group term (HLGT), high-level term (HLT), preferred term (PT), and lower-level term (LLT) will be provided in the AE dataset.

#### **7.1.2. Adverse Event Severity**

Adverse events are graded by the investigator as Grade 1, 2, 3, or 4 according to the toxicity criteria specified in the protocol. The severity grade of events for which the investigator did not record severity will be categorized as “missing” for tabular summaries and data listings. The missing category will be listed last in summary presentation.

#### **7.1.3. Relationship of Adverse Events to Study Drug**

Related AEs are those for which the Investigator selected “Related” on the AE eCRF to the question of “Relationship to Study Treatment” based on the his/her clinical assessment. Events for which the Investigator fails to record a relationship to an applicable study drug will be considered related to study drug for summary purposes. However, by-subject data listings will show the relationship as missing.

#### **7.1.4. Serious Adverse Events**

Serious adverse events (SAEs) will be identified and captured as SAEs if the AEs met protocol-specified definitions of a SAE.

#### **7.1.5. Treatment-Emergent Adverse Events**

##### **7.1.5.1. Definition of Treatment-Emergent Adverse Events**

Treatment-emergent adverse events (TEAEs) are defined as any AEs with an onset date/time equal to or after the study drug start date/time through end of study .

##### **7.1.5.2. Incomplete Dates**

If the onset date of the AE is incomplete and the AE stop date is not prior to the first dose date of any study drug, then the month and year (or year alone if month is not recorded) of onset determine whether an AE is treatment emergent. The event is considered treatment emergent if both of the following 2 criteria are met:

- The AE onset date is in the same as or after the month and year (or year) of the first dose date of any study drug, and
- The AE onset date is in the same as or before the month and year (or year) of the end of study

An AE with completely missing onset and stop dates, or with the onset date missing and a stop date later than the first dose date of any study drug, will be considered to be treatment emergent. In addition, an AE with the onset date missing and incomplete stop date with the same or later month and year (or year alone if month is not recorded) as the first dose date of any study drug will be considered treatment emergent.

#### **7.1.6. Summaries of Adverse Events and Deaths**

Treatment-emergent AEs will be summarized based on the Safety Analysis Set. Tables will be created per study phase (i.e. On-Treatment Phase, Off-Treatment Phase, and NrtI-Restart Phase).

A brief, high-level summary of the number and percentage of subjects who experienced at least 1 TEAE in the categories described below will be provided by treatment group. The brief summary will also include treatment-related TEAEs, treatment-related TE SAEs, and TEAEs leading to premature study discontinuation. All deaths observed in the study will also be included in this summary. In addition, a table for each category showing the number and percentage of subjects will be provided by PT and treatment group in descending order of total frequency:

- TEAEs
- TEAEs by severity grade
- TEAEs related to AB-729
- TEAEs related to VBR
- TE SAEs
- TE SAEs related to AB-729
- TE SAEs related to VBR
- TEAEs leading to premature study drug AB-729 discontinuation
- TEAEs leading to premature study drug VBR discontinuation
- TEAEs leading to study discontinuation
- TEAEs leading to death (ie, outcome of death)

- COVID-19 specific TEAEs
- COVID-19 specific TE SAEs

Multiple events will be counted only once per subject in each summary. For summary by severity grade, the most severe grade will be used for those AEs that occurred more than once in an individual subject during the study.

A data listing containing all AEs will be provided.

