#### **2.3.3.2 Study AB-729-001 Preliminary Safety**

In Part 2 of Study AB-729-001, preliminary safety data are available for Cohort A (180 mg single dose), Cohort B (60 mg single dose), and Cohort C (90 mg single dose). There have been no deaths, SAEs, or AEs leading to discontinuation. In Cohort A, 8 TEAEs were observed in 4 subjects including 5 related AEs (Grade 1 ALT [n=2] and AST; Grade 2 headache [n=2]). One subject had an unrelated Grade 2 foodborne toxic illness that was accompanied by Grade 3 ALT and AST changes (without bilirubin changes or changes in markers of liver synthetic function), which returned to baseline levels. In Cohort B, 6 Grade 1 TEAEs have been observed in 3 subjects, including 2 related AEs of Grade 1 injection site redness and injection site pruritis, both transient.

In Cohort C, 8 Grade 1 or 2 TEAEs have been observed in 6 subjects, including 5 related AEs of Grade 1 or 2 injection site pain lasting less than 1 hour (including 2 subjects whose doses were split into 2 injections erroneously). There were no other clinically significant changes in laboratory parameters, ECGs, vital signs, or physical exam findings.

In Part 3 of Study AB-729-001, preliminary safety data are available for Cohort E (60 mg administered every 4 weeks) and Cohort F (60 mg administered every 8 weeks). There have been no deaths, SAEs, or AEs leading to discontinuation. In Cohort E, 7 Grade 1 or 2 TEAEs have been observed in 4 subjects, including 4 related Grade 1 injection site AEs (bruising and transient redness) and 2 related Grade 1 ALT elevations. In Cohort F, 2 Grade 1 TEAEs have been observed in 2 subjects, both related (fatigue and injection site redness). There were no other clinically significant changes in laboratory parameters, ECGs, vital signs, or physical exam findings.

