### **8.8.5 Injection Site Reaction Diary**

Subjects enrolled in Groups 1 and 3 will be provided an injection site reaction diary to capture information regarding the nature of any changes at the site of the AB-729 subcutaneous injection(s) occurring while as an outpatient, including the resolution of these events. These subjects will be instructed to contact the clinical site with any new AEs they observe at the injection site(s) to determine if an unscheduled clinic visit is needed for formal assessment of the AEs.

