##### **10.4.5.1 Adverse Events**

Adverse events will be coded using the Medical Dictionary for Regulatory Activities (MedDRA). A TEAE will be defined as any AE that begins on or after the date of first dose of study drug through end of study (completion of follow-up period or “lost to follow-up”).

Summaries (number and percentage of subjects) of TEAEs by system organ class and preferred term will be provided by treatment group. Summaries will include all TEAEs, TEAEs considered related to study treatment by investigators, TEAEs by Grade, and SAEs. All AEs, emergent or nonemergent, will be listed by subject. Any TEAEs leading to premature discontinuation from the study intervention and serious TEAEs will be presented as a separate table or a listing.

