## **7.6. Other Safety Measures**

Since the study is terminated early, no additional safety measures specified in the protocol will be performed.

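### SAP 7.1.6 tabulates TEAEs by preferred term only, so no planned summary gives the proportion of AB-729 recipients with any injection-site reaction

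*Combined protocol and SAP*

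**What the plan says.** SAP 7.1.6 starts with a high-level summary of subjects with at least one TEAE in each of a set of categories: any, by grade, related to each drug, serious, leading to discontinuation, fatal and COVID-19 specific. For each category it then plans a table "showing the number and percentage of subjects will be provided by PT and treatment group in descending order". It adds: "A data listing containing all AEs will be provided".

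Protocol 10.4.5.1 describes a different layout: "Summaries (number and percentage of subjects) of TEAEs by system organ class and preferred term will be provided by treatment group". SAP 7.1.1 keeps the higher dictionary levels available, since SOC, high-level group term (HLGT), "high-level term (HLT), preferred term (PT), and lower-level term (LLT) will be provided in the AE dataset". No planned table uses a level above PT.

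Protocol 8.8.5 sets up dedicated collection: "Subjects enrolled in Groups 1 and 3 will be provided an injection site reaction diary to capture information". Protocol 8.3.3 has the diary reviewed at Weeks 2, 12, 20, 28, 36 and 44, and protocol 8.5 lists it at the Premature Termination visit. The SAP mentions neither the diary nor injection-site reactions. Its references to injections concern exposure and compliance (SAP 4.2). Citing early termination, SAP 7.6 states that "no additional safety measures specified in the protocol will be performed".

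**The concern.** The primary objective is the safety and tolerability of the combination. For a drug given by six subcutaneous injections, a reader of the report will want to know how many recipients had any injection-site reaction, and whether the triple arm (Group 1) differs from AB-729+NrtI (Group 3) on it.

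A table by PT does not answer that directly. A subject with redness after one dose and pruritus after another is counted once in each of two rows, and no row counts that subject once for either. The nearest planned figure, subjects with a TEAE related to AB-729, also takes in liver enzyme rises and other events, and it depends on the investigator's causality call.

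**Working it through.** The plan states no figure to reproduce. The check has three parts.

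**1. How prominent are injection-site events?** The counts are the related adverse events in protocol 2.3.3.2. For example, Cohort B is described as "including 2 related AEs of Grade 1 injection site redness and injection site pruritis, both transient".

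| Cohort | AB-729 dose | Related events | Injection-site | Other |
|---|---|---|---|---|
| A | 180 mg single | 5 | 0 | 2 ALT, 1 AST, 2 headache |
| B | 60 mg single | 2 | 2 (redness, pruritus) | 0 |
| C | 90 mg single | 5 | 5 (pain) | 0 |
| E | 60 mg every 4 weeks | 6 | 4 (bruising, redness) | 2 ALT |
| F | 60 mg every 8 weeks | 2 | 1 (redness) | 1 fatigue |
| Total | | 20 | 12 | 8 |

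- All cohorts: 12/20 = 60% injection-site. The next type is ALT/AST, with 3 + 2 = 5, so 5/20 = 25%.
- At 60 mg, the dose level of this trial (B, E, F): (2 + 4 + 1)/(2 + 6 + 2) = 7/10 = 70%, all Grade 1.
- Types at 60 mg: redness, pruritus and bruising. Pain was reported only in Cohort C, at 90 mg, and was Grade 1 or 2.

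These are counts of events, not of subjects.

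**2. What do PT rows leave undetermined?** Let n_j be the number of subjects in a group with injection-site PT j, and N the group size. The number with any such reaction satisfies

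max(n_j) ≤ n_any ≤ min(N, Σ n_j).

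The lower limit is reached when every affected subject also has the most common term, and the upper limit Σ n_j when no subject has two terms. The rows fix n_any only if at most one injection-site PT occurs.

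The protocol's own summary shows a similar gap. It gives events by type but not subjects with any reaction. At 60 mg, a related injection-site event affected at least 1 + 1 + 1 = 3 subjects and at most 2 + 4 + 1 = 7. With the cohort sizes in protocol 2.3.3.1 (6 + 7 + 7 = 20), that is 3/20 = 15% to 7/20 = 35%.

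**3. Would restoring SOC be enough?** No. In the hierarchy listed in SAP 7.1.1 (SOC, HLGT, HLT, PT), SOC stands three levels above PT and is too broad to isolate the injection site. Restoring it brings the SAP into line with the protocol. The any-reaction count needs a grouped row, defined by HLT or by a listed set of PTs.

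**The case against.** The strongest case on the other side is that nothing is lost. The SAP plans a listing of all adverse events and keeps the coded levels in the dataset. With about 45 AB-729 recipients planned (30 + 15), the count can be derived afterwards. The protocol's statistical section promises no injection-site summary either, so only the SOC level is a departure from it. The reduced scope is deliberate and disclosed: the study was terminated early, SAP 1 limits the analyses to key safety and efficacy endpoints, and the output is a Synoptic CSR. The known events were mild, with no serious events and no discontinuations for adverse events. At this trial's regimen (Cohort F, 7 subjects) there was one injection-site event.

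Most of this stands, and it limits the weight of the point. It does not remove it. Safety is the primary objective, SAP 1 says that every active subject completed the 48-week treatment period, and SAP 7.1.6 already makes room for COVID-19 rows.

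Four stronger readings are tempting, and the documents do not support them:
- A reader might infer that the report could not give the figure at all. The listing and dataset would allow it; only a planned summary is missing.
- A reader might take SAP 7.6 to remove injection-site events from the analysis. Reactions recorded as adverse events still enter the SAP 7.1.6 tables and listing.
- A reader might assume a count for each of several PTs and quote a wide range as the size of the problem. The documents give no such counts for this trial.
- A reader might extend the argument to rash. Protocol 2.2.3.2 reports rash as one term (5/92), nothing shows it being split, and the rash that led to discontinuation in Study 211 began in Study 201.

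**Conclusion.** The point holds as a reporting gap of minor to moderate weight. SAP 7.1.6 departs from protocol 10.4.5.1 by dropping SOC, and no planned summary gives the proportion of AB-729 recipients with any injection-site reaction. That is the most frequent related event type in the protocol's AB-729 data by event count (12/20 overall, 7/10 at 60 mg). The size of the gap in this trial cannot be stated in advance; PT rows would give only the bounds shown above.

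The conclusion assumes that different manifestations are coded to different PTs. The documents do not show the coding, but they point that way: protocol 2.3.3.2 names the manifestations separately, and Appendix 1 grades injection-site pain, redness, swelling and pruritus as separate parameters. If all were coded to one general term, that row would already be the any-reaction count. The preliminary data are small and count events, so they show which type is common and do not predict a rate here. Clinical management is not affected.

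**What to change.** In SAP 7.1.6:

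1. Present TEAEs by SOC and PT, as protocol 10.4.5.1 states, or record the reason for using PT alone.
2. Add one prespecified row, 'any injection-site reaction', for Groups 1 and 3. Define it by HLT or by a listed set of PTs, and check the definition against the coded data so that terms such as bruising at the injection site are not missed. Count each subject once, at worst grade.

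The cost is a sentence or two of SAP wording and one or two extra table rows. The codes are already in the adverse event dataset, so no new data are needed. If the SAP is already final, SAP 1 provides for recording the change in the Synoptic CSR.
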